7.2.6. Pharmacokinetic Concentration Analyses

Plasma concentrations of total Mo and PUF Mo (as surrogate measures of ALXN1840 PK) and time data will be presented in a data listing by patient. Plasma concentration data will be summarized separately by analyte, day, and time point using descriptive statistics. When calculating the geometric mean, values of 0 will be discarded.

Mean plasma concentration versus scheduled time profiles will be presented in figures on both linear and semilogarithmic scales. Individual plasma concentration versus actual time profiles will be presented similarly. The time to reach steady state will be graphically assessed by plotting mean plasma trough (pre-dose) concentration observed at the start of the dosing interval (C_{trough}) concentration versus study day in both linear and semilogarithmic scales. Additionally, time to steady state will be evaluated using stepwise testing for linear trend.

7.2.7. Pharmacokinetic Parameter Analyses

The following plasma PK parameters, as data permit, will be calculated for total Mo and PUF Mo on Week 6 (Day 43) and Week 36 (Day 253) using noncompartmental methods with Phoenix[®] WinNonlin[®] (Certara USA Inc., Princeton, New Jersey) version 8.0 or higher or SAS[®] version 9.4 or higher (SAS Institute Inc., Cary, North Carolina), as applicable. Calculations will be based on the actual sampling times relative to the actual reference ALXN1840 dosing times recorded during the study.

- Time delay between the time of dosing and time of appearance of Mo concentration (T_{lag}) in plasma (Week 6 [Day 43] and Week 36 [Day 253])
- Maximum observed concentration (C_{max}) (Week 6 [Day 43] and Week 36 [Day 253])
- Time to maximum concentration (T_{max}) (Week 6 [Day 43] and Week 36 [Day 253])
- Trough (pre-dose) concentration observed at the start of the dosing interval (C_{trough})
- Time of the last quantifiable concentration (T_{last}) (Week 6 [Day 43] and Week 36 [Day 253])
- Observed concentration at the end of the dosing interval (C_{τ} , where $\tau = 24$ h) (Week 6 [Day 43] and Week 36 [Day 253])

- Area under the plasma concentration versus time curve (AUC) from time 0 to the last quantifiable concentration (AUC_t) (Week 6 [Day 43] and Week 36 [Day 253])
- AUC over the dosing interval (AUC_τ) (Week 6 [Day 43] and Week 36 [Day 253])
- Accumulation ratio (AR) calculated as C_{max} , C_{trough} , and AUC_τ after repeat dosing on Week 36 (Day 253) divided by those after the initial dosing on Week 6 (Day 43):
 - $C_{max,Day253}/C_{max,Day43}$
 - $C_{trough,Day253}/C_{trough,Day43}$
 - $AUC_{\tau,Day253}/AUC_{\tau,Day43}$

Additional plasma PK parameters may be calculated if deemed appropriate.

Pharmacokinetic parameters derived from plasma concentrations of total Mo and PUF Mo will be presented in data listings and summarized by analyte and day using descriptive statistics.

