4. STUDY DESIGN

4.1. Overall Design

This is a Phase 2, open-label multicenter study designed to evaluate the change in liver Cu concentration following 48 weeks of treatment with ALXN1840 at doses up to 30 mg/day in adult patients with WD who have previously been treated for at least 1 year with SoC (ie, trientine, penicillamine, or zinc).

On Day 1 of the Treatment Period, patients will receive ALXN1840. Patients will be initiated at 15 mg once daily, then the dose will be increased to 30 mg once daily at Week 6.

In case of drug tolerability issues, the dose of ALXN1840 may be reduced or temporarily interrupted. Such dose changes must be discussed with the Alexion Medical Monitor and documented in the study record. Any subsequent dose increases must be approved by Alexion.

The planned study duration is approximately up to 100 weeks, including a 4-week Screening Period. A liver biopsy will be performed during the Screening Period within 14 days prior to the first dose of study drug, followed by a 48-week Treatment Period, which starts on the day of first dose of study drug. Patients who complete the 48-week Treatment Period will be offered the opportunity to participate in a 48-week Extension Period to evaluate the long-term safety and efficacy of ALXN1840.

This study is pathologist-blinded for the assessments of liver histology samples.

If additional clinical evaluation outside of the visit schedule is deemed necessary by the Investigator, or if the patient meets dose modification criteria, then unscheduled visits can occur. Additionally, if there is clear neurological deterioration, as demonstrated by signs or symptoms of neurological worsening, then additional neurological assessments will be performed at the discretion of the Investigator.

An independent Data Monitoring Committee (DMC), comprising experts in relevant fields with no direct relationship to the study, will be appointed by Alexion to review and monitor study data for safety, effectiveness, and study conduct, and make recommendations regarding study continuation, changes to the study population, and/or modification to study procedures. Further details are provided in [Section 9.5](#).

An independent Hepatic Adjudication Panel, comprising experts in relevant fields will be appointed by Alexion. Details of the Hepatic Adjudication Panel are provided in [Section 9.6](#).

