6.1. Study Drugs Administered

Details of the study drug to be administered in this study are detailed in [Table 5](#).

Table 5: Study Drugs Administered

Drug Name	ALXN1840
Type	Drug
Dose Formulation	White, round, delayed-release tablet
Unit Dose Strength(s)	15 mg
Dosage Level(s)	15 mg daily up to 30 mg daily
Route of Administration	Oral
Use	Experimental
IMP and NIMP	IMP
Sourcing	Provided centrally by Alexion
Packaging and Labeling	ALXN1840 will be provided in treatment kits that will each have a unique identification number and be packaged and labelled in accordance with all applicable regulatory requirements. At a minimum, the treatment kit label will provide the following information: study Sponsor identification, batch number, directions for use, required storage conditions, caution statements (including “New Drug-Limited by Federal Law to Investigational Use” language), study identification, and expiry date.
Current/Former Name(s) or Alias(es)	bis-choline tetrathiomolybdate

Abbreviations: IMP = investigational medicinal product; NIMP = Noninvestigational medicinal product

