8.5. Pharmacokinetics

- Blood samples will be collected for measurement of total and PUF Mo in plasma at the time points specified in the SoAs ([Table 1](#) and [Table 2](#)).
- A maximum of 5 samples may be collected at additional time points during the study if warranted and agreed upon between the Investigator and Alexion. The timing of sampling may be altered during the course of the study based on newly available data (eg, to obtain data closer to the time of peak plasma concentrations) to ensure appropriate monitoring.
- Instructions for the collection and handling of biological samples will be provided by Alexion. The actual date and time (24-hour clock time) of each sample will be recorded.
- Samples will be used to evaluate the PK of ALXN1840. Samples collected for analyses of total and PUF Mo may also be used to evaluate safety or efficacy aspects related to concerns arising during or after the study.

- Samples will be used for diagnostic biomarker development and research to understand the pathways associated with disease states and the mechanism of action of ALXN1840.

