7.2.5.1. Pharmacokinetic and Pharmacodynamic Sampling

In the Treatment and Extension Periods, plasma samples will be obtained from the blood samples collected pre-dose on the day of all study visits. Patients will be instructed not to take their dose of ALXN1840 on the morning of scheduled study visits, so that PK/PD/biomarker samples are collected at pre-dose trough for measuring total and PUF Mo (PK), total and PUF Cu, cNCC/NCC_{corrected}, dNCC, LBC (PD), Cp, and CpC (biomarker). Additional measurements on ALXN1840 PK/PD including Mo and Cu in the tripartite complexes (TPCs) may be conducted.

In the Treatment Period, at the Week 6 (Day 43) and Week 36 (Day 253) Visits, serial blood samples will be collected for plasma PK/PD/biomarker concentrations at the following time points: pre-dose at 0 hour, and at 2- and 4-hours post-dose.

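### SAP 7.2.7 lists an observed 24 h concentration, a 24 h AUC and a lag time for Week 6 and Week 36, but the serial plasma samples stop at 4 h

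*SAP*

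**What the plan says.** Protocol Section 3 (Table 4) gives the secondary PK objective three endpoints: plasma profiles at Week 6 and Week 36, pre-dose troughs at site visits, and concentrations in the liver biopsy.

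For the profiles, the notes to the protocol's Schedule of Activities and SAP 7.2.5.1 agree on the sampling times: "pre-dose at 0 hour, and at 2- and 4-hours post-dose". Neither schedules a later sample.

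SAP 7.2.7 says that parameters, "as data permit, will be calculated for total Mo and PUF Mo", will be derived on both days. The list includes:
- the lag time, "Time delay between the time of dosing and time of appearance of Mo concentration";
- C-tau, "Observed concentration at the end of the dosing interval", with tau set to 24 h;
- "AUC over the dosing interval" (AUC-tau), and AUC to the last quantifiable concentration;
- Cmax, Tmax and Tlast;
- Day 253/Day 43 accumulation ratios for Cmax, C-trough and AUC-tau, with the Week 6 dose described as the initial one.

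On dosing, Protocol 4.1 says: "Patients will be initiated at 15 mg once daily, then the dose will be increased to 30 mg once daily at Week 6". Protocol 6.6 places that step at Day 43. Protocol 6.1 describes the product as a "White, round, delayed-release tablet".

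**The concern.** Several listed parameters need information that the schedule does not collect. The SAP gives no rule for filling the gap, neither a substitution of the pre-dose value nor an extrapolation. A programmer must therefore leave C-tau and AUC-tau blank or choose an unstated assumption, and the natural choice does not suit the first of the two days.

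The lag time has a different problem. Its definition relies on molybdenum appearing in plasma, but by Day 43 patients have been dosed since Day 1. A lag of zero produced by drug carried over from earlier doses could be read as a property of a delayed-release tablet.

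The accumulation ratios inherit both problems and also compare two days across a planned dose step. At stake is the accuracy of the PK tables that report a named secondary endpoint. The primary liver-copper analysis does not depend on them.

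**Working it through.** The documents state no PK precision figure and no PK constants, so there is no figure of the plan's own to reproduce. The check compares each parameter with the sampling times.

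**Coverage.** 4/24 = 16.7% of the interval is sampled; 24 - 4 = 20 h are not.

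| Parameter | Needs | Schedule gives |
|---|---|---|
| C-tau, observed | a sample at 24 h | none after 4 h |
| AUC-tau | values to 24 h, or a terminal slope (normally at least 3 points) | 2 post-dose points |
| Lag time | Mo absent pre-dose and close sampling after it | pre-dose after 42 days of dosing, then a 2 h grid |
| Tmax, Tlast | samples around and after the peak | Tmax nominally 0, 2 or 4 h; Tlast at most 4 h |
| AUC-t | quantifiable samples | in effect AUC0-4h |

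**Pre-dose value used at 24 h.** With C0, C2 and C4 the three concentrations, the linear trapezoidal rule gives

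AUC-tau = 2(C0+C2)/2 + 2(C2+C4)/2 + 20(C4+C0)/2 = 11·C0 + 2·C2 + 11·C4.

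One straight line carries 20 of the 24 h. At steady state on an unchanged dose, C-tau equals the pre-dose value, so the end point at least is sound.

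On Day 43 it is not, if the 30 mg dose is the one taken between the pre-dose and 2 h samples. For a linear one-compartment drug at steady state on 15 mg, with absorption complete by 24 h,

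C-tau / pre-dose = 2 - 2^(-24/half-life).

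Assumed half-lives of 6, 12, 24, 48 and 72 h give 1.94, 1.75, 1.50, 1.29 and 1.21. The pre-dose value is too low as a 24 h value in every case.

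**Illustration on assumed constants.** One-compartment model with lag; half-life 6-72 h, absorption rate 0.3 or 1.0 per h, lag 0.5, 2 or 3 h (30 settings):

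| | Week 36 | Day 43, 30 mg given |
|---|---|---|
| AUC0-4h as share of true AUC-tau | 7-28% | 5-27% |
| AUC-tau by pre-dose substitution, as share of true | 65-126% | 52-121% |
| Observed Cmax as share of true | 56-100% | 50-100% |
| True Tmax after 4 h | 25 of 30 (83%) | 26 of 30 (87%) |

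The last two rows depend heavily on the grid. With half-life 12-48 h, absorption rate 0.3-1.0 per h and lag 1-3 h, Tmax falls after 4 h in 25 of 27 settings, and observed Cmax is 66-100% of true (median 93%). With the same half-lives but absorption rate 1-2 per h and lag 0.5-2 h, it does so in only 7 of 27, and observed Cmax is 96-100% of true.

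**Accumulation ratios.** Under linear PK, a pre-dose value at steady state on 15 mg (Day 43) and one at steady state on 30 mg (Day 253) have a ratio of 30/15 = 2 with no further accumulation. Linearity is an assumption: Protocol 2.2.2 reports no clear dose proportionality in the earlier Phase 2 study.

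**The case against.** The strongest reply has five parts.

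- **The list is hedged.** Parameters are calculated only as data permit, so a blank AUC-tau is the rule working. This holds for occasional missing samples. It does not justify listing a parameter whose 24 h value no patient is scheduled to provide.
- **More samples are possible.** Protocol 8.5 allows up to five extra samples and altered timing, for example "to obtain data closer to the time of peak plasma concentrations". These are discretionary and none is scheduled. The clause is conditional on new data, so it does not concede that the peak will be missed.
- **Derivation rules may sit elsewhere.** Protocol 9.4.3 mentions a PK/PD data analysis plan, as applicable, which is not available here. Even so, the SAP list calls C-tau observed, and a rule elsewhere would not make it so.
- **Steady state will be examined.** SAP 7.2.6 plans trough plots and stepwise trend testing. That supports pre-dose substitution at Day 253, and this part of the objection stands. A reader might infer that AUC-tau is unobtainable for every patient on both days; that goes too far.
- **Cmax and AUC-t are already defined by what is observed.** This also stands, as it does for Emax and AUEC-t in SAP 7.2.9. A label stating the 0-4 h range clarifies these definitions and corrects no error.

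A reader might also infer that the report will show a lag time of zero throughout. The documents do not say that Mo will be quantifiable pre-dose. Total Mo and ultrafiltrate Mo may differ, and SAP 7.2.5.2 provides for values below quantification before the first measurable one.

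**Conclusion.** The mismatch is real and rests on the text alone: on both profile days the SAP lists an observed 24 h concentration, a 24 h AUC and a lag time that samples at 0, 2 and 4 h do not support. An approximate 24 h AUC is available at Day 253 if steady state holds on an unchanged once-daily dose. It is not available on Day 43, given the planned dose change that day. The lag time is not identifiable where pre-dose Mo is quantifiable (it would return 0), and otherwise is resolved only to 2 h.

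Two stronger conclusions are tempting and not supported. One is that the whole secondary PK objective fails; the trough and liver-concentration endpoints do not use the 2 h and 4 h samples. The other is that Cmax is materially understated and the true peak falls after 4 h; the documents give no half-life, absorption rate or lag, and the answer changes with the constants assumed.

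The analyses are descriptive, so no test or sample size is affected. The SAP should still be corrected, because it lists parameters for a secondary endpoint that the schedule cannot deliver.

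**What to change.** In SAP 7.2.7 and its table shells:

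1. Delete the lag time and the observed C-tau.
2. Replace AUC-tau by AUC0-4h, shown with the pre-dose, 2 h and 4 h concentrations.
3. Footnote that Cmax and Tmax are maxima within 0-4 h.
4. If a 24 h AUC is kept, derive it at Day 253 only, in patients at steady state on an unchanged once-daily dose, using the pre-dose value at 24 h, and label it approximate.
5. Delete the AUC-tau accumulation ratio, which would have no Day 43 denominator.
6. Present the Cmax and C-trough ratios as Day 253/Day 43 ratios across a planned dose change. Do not call them accumulation after a first dose, since patients have been dosed since Day 1.
7. Reconcile the passages on sampling times, the Day 43 dose and the parameter list, so that it is clear which dose the Week 6 profile follows.

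A 0-4 h label on Emax, TEmax and AUEC-t in SAP 7.2.9 is optional.

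The cost is SAP wording and table shells, with no new samples. The downside is that fewer PK parameters are reported.

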Pregnancy test ^m	X	X			X		X	X	X	X		X		X		X	
Chemistry, coagulation, hematology panel, and urinalysis ⁿ	X ^o	X			X	X	X	X	X	X		X		X ^p		X	
Screening ultrasound (before liver biopsy)	X																
MRE, transient elastography (FibroScan preferred), MR-PDF	X													X			
Optical coherence tomography	X													X			
Liver biopsy (see Section 5.3.2)	X													X			
Plasma PK/PD/biomarker samples ^q		X			X	X	X	X	X	X		X		X			
24-hour urine ^r		X			X			X		X		X		X			
UWDRS ^{s,t}		X												X			
CGI ^s		X ^u			X			X		X		X		X			
EQ-5D ^s		X								X				X			
TSQM-9 ^s	X													X			

- ⁿ The MELD and modified Nazer scores will be calculated by a central laboratory.
- ^o In addition to screening samples submitted to the central laboratory, additional samples for coagulation and hematology tests are to be performed at a local laboratory within 3 days before the liver biopsy, to assure the safety of the liver biopsy.
- ^p Plasma samples will be obtained from the blood samples collected pre-dose on the day of all study visits. Patients should be instructed not to take their dose of ALXN1840 on the morning of scheduled study visits so that PK/PD/Biomarker samples are collected at pre-dose trough: total and PUF Mo (PK), total and PUF Cu, NCC (PD), Cp, and CpC (biomarker). At the Week 6 (Day 43) and Week 36 (Day 253) visits, serial blood samples will be collected for plasma PK/PD/Biomarker concentrations at the following time points: pre-dose at 0 hour, and at 2- and 4-hours post-dose.
- ^q For the 24-hour urine sample, 500 mL will be considered the minimum acceptable sample size. Any amount < 500 mL will not be tested due to an insufficient sample collection. Urine collected will be used for 24-hour creatinine, Mo and Cu. Dispense container for 24-hour urine collection during the Screening Period, Day 1, and Day 57 (Week 8), Day 127 (Week 18), Day 169 (Week 24), and Day 253 (Week 36).
- ^r The UWDRS is scheduled to be performed at Day 1 and Day 337 (Week 48) only but can also be performed as appropriate if a neurological adverse event is reported.
- ^s Can be performed up to 7 days before Day 1, at the discretion of the Investigator.
- ^t CGI-I is not performed at Day 1, only CGI-S.
- ^u Adverse event, concomitant medication, and non-pharmacologic therapy/procedure are to be collected from signing of the ICF.

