4.3. Justification for Dose

For this study, the term “dose” refers to the following:

Dosing for ALXN1840 will be initiated at 15 mg once daily, then the dose will be increased to 30 mg once daily at Week 6.

A starting dose of 15-60 mg daily was shown to have an acceptable safety profile and was effective in reducing NCC in a Phase 2 study in patients with WD (Weiss, 2017). Elevation of hepatic transaminases and/or gamma glutamyl transferase occurred in 39% of patients in the Phase 2 study and were generally associated with higher doses of ALXN1840. Elevations of

liver enzymes were detected by routine laboratory monitoring and were managed by dose reduction or treatment interruption of ALXN1840. In this study, the starting dose will be 15 mg once daily for the first 6 weeks, then the dose will be titrated up to 30 mg once daily. Elevation of liver enzymes, if occurring, and management of other laboratory abnormalities or AEs, will be managed according to [Table 6](#). Any change to dosing in response to laboratory results or AEs must be discussed with the Alexion Medical Monitor and documented in the study record. Subsequent dose increases must be approved by Alexion.

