6.6. Dose Modification

Patients will be initiated on ALXN1840 at 15 mg once daily, then the dose will be increased to 30 mg once daily at Week 6 (Day 43).

The dose should be decreased or interrupted if any of the relevant Dose Modification Criteria are met (see [Table 6](#)). Deviation from the dose modification guidelines must be agreed with the Alexion Medical Monitor. Any subsequent dose increases must be approved by Alexion.

All patients will continue to be treated with ALXN1840 in the Extension Period at the same dose they received at the last study visit in the Treatment Period and ALXN1840 administration during the Extension Period will follow the same procedures as for the Treatment Period.

In case a dose modification is necessary for ALXN1840, it will be administered as per the details in [Table 6](#).

Table 6: ALXN1840 Dose Modifications for Individual Patients

Test	Result	Conditions	Action with ALXN1840 Dosing	Changes in Safety Monitoring ^a	Re-Challenge ^b
ALT	> 5 × ↑ from baseline	ALT above reference range at baseline	Temporary interruption	Contact patient within 48 hours to arrange repeat testing Weekly repeat testing	At 15 mg QOD when ALT < 2 × ↑ from baseline.
	> 5 × ULN	ALT within reference range at baseline	Temporary interruption	Contact patient within 48 hours to arrange repeat testing Weekly repeat testing	At 15 mg QOD when ALT < 2 × ULN.
	> 2 × ↑ from baseline	ALT above reference range at baseline	Reduce dose to previous dose level if up-titration has occurred or reduce dose to 15 mg QOD if on 15 mg QD. No further dose ↑ until resolution of abnormality.	Weekly repeat testing	Not applicable.
	> 2 × ULN	ALT within reference range at baseline	Reduce dose to previous dose level if up-titration has occurred or reduce dose to 15 mg QOD if on 15 mg QD. No further dose ↑ until resolution of abnormality.	Weekly repeat testing	Not applicable.
Increased triglycerides	> 300 to 500 mg/dL or > 3.4 to 5.6 mmol/L	None	Reduce dose to previous dose level if up-titration has occurred or reduce dose to 15 mg QOD if on 15 mg QD. No further dose ↑ until resolution of abnormality.	Weekly repeat testing	Not applicable
	> 500 mg/dL or 5.6 mmol/L		Temporary interruption		At 15 mg QOD when triglyceride concentrations return to baseline

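### The Day 253/Day 43 ratios in SAP 7.2.7 are labelled accumulation, but Day 43 is not initial dosing: it follows six scheduled weeks at 15 mg daily and is the day the dose rises

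*SAP*

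**What the plan says.** SAP 7.2.7 lists an accumulation ratio for total and ultrafiltrate molybdenum (Mo). Cmax, Ctrough and AUC over the dosing interval on Day 253 are each "divided by those after the initial dosing on Week 6 (Day 43"). The same section defines Ctrough as a pre-dose value, makes all parameters conditional ("The following plasma PK parameters, as data permit, will be calculated for total Mo and PUF Mo"), and summarises them by analyte and day.

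The protocol's dosing schedule reads differently:
- Section 4.1: "Patients will be initiated at 15 mg once daily, then the dose will be increased to 30 mg once daily at Week 6", with dosing starting on Day 1.
- Section 4.3: "the starting dose will be 15 mg once daily for the first 6 weeks".
- Section 6.6: "then the dose will be increased to 30 mg once daily at Week 6 (Day 43").
- Section 1.3, Table 1 footnotes: "Patients should be instructed not to take their dose of ALXN1840 on the morning of scheduled study visits", so that the visit sample is a pre-dose trough.

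Serial samples are scheduled only at Weeks 6 and 36, at 0, 2 and 4 h (SAP 7.2.5.1). There is no serial profile on Day 1.

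**The concern.** An accumulation ratio normally sets exposure after repeated dosing against exposure after a first dose of the same size. Here the denominator visit is neither a first dose nor, for the trough, at the same scheduled dose as the numerator. A reader of the study report who sees a trough ratio near 2 under this label would conclude that the drug roughly doubles on repeated dosing, when the figure may show only that the dose was doubled.

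The summary adds a second difficulty. Protocol Table 6 allows interruptions, reductions and re-challenge at 15 mg every other day. Patients with quite different doses behind the two samples would enter one mean.

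**Working it through.** **Timing.** SAP 9.4.4 sets the target day at 7 × week + 1, giving 7 × 6 + 1 = 43 and 7 × 36 + 1 = 253. Day 43 therefore follows 43 − 1 = 42 scheduled days at 15 mg daily.

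**What stands behind each term, on schedule.**
- Day 43 trough: repeated 15 mg daily only, because it precedes that day's dose.
- Day 43 Cmax and AUC: on the natural reading, the first 30 mg dose plus what remains from 15 mg dosing.
- Day 253 values: whatever dose and frequency the patient has at Week 36.

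The labelling error follows from these passages alone. The plan states no figure to reproduce, so the sizes below are illustrations.

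**Assumptions, none given in the documents.** Linear one-compartment kinetics, absorption rate 1/h, no absorption lag unless stated, half-life h of 6, 24 or 120 h, no time effect, and negligible pre-treatment Mo. The fraction left after 24 h is r = 0.5^(24/h) = 0.0625, 0.50 and 0.871.

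**Trough ratio.** At steady state the trough on dose D daily is proportional to D·r/(1 − r).
- 15 mg daily before Day 43, 30 mg daily at Week 36: 30/15 = 2. The full model gives 2.00, 2.00 and 2.01.
- 15 mg daily at both: 1.00.
- 15 mg daily before Day 43, 15 mg every other day at Week 36, sampled 48 h after the last dose: [r²/(1 − r²)] / [r/(1 − r)] = r/(1 + r) = 0.06, 0.33 and 0.47.
- Every other day from Day 29, with the Day 43 sample 48 h after the last dose, then 30 mg daily: 2(1 + r)/r = 34, 6.0 and 4.3 at steady state. The full model, with only two weeks on that regimen, gives 34, 6.0 and 3.7.

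**Pooling.** If half the patients are in the first group and half in the third (assumed shares), the geometric mean ratio is √(2.0 × 0.059) = 0.34 at a 6 h half-life and √(2.0 × 0.467) = 0.97 at 120 h.

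**24 h AUC ratio, if the first 30 mg dose is on Day 43.** Let A be the 24 h AUC of a single first 30 mg dose and R the true accumulation. The numerator is R·A. The denominator is A plus half of the 30 mg carry-over, A + (R − 1)A/2 = A(1 + R)/2. The ratio is 2R/(1 + R), which cannot exceed 2.
- h = 6: R = 1.08, ratio 2.16/2.08 = 1.04.
- h = 24: R = 2.06, ratio 4.12/3.06 = 1.35.
- h = 120: R = 8.04, ratio 16.08/9.04 = 1.78.

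**Cmax ratio.** From samples at 0, 2 and 4 h it runs from 1.04 to 1.80 with a lag of 0 to 2 h. With a 4 h lag the highest sample is the pre-dose one, and the ratio becomes the trough ratio, 2.00 to 2.01. The product is a delayed-release tablet (Protocol 6.1), so a lag is plausible.

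**Pre-treatment Mo.** If it equals a fraction b of the 15 mg trough, the first trough ratio becomes (2 + b)/(1 + b) = 1.91, 1.67 and 1.50 for b = 0.1, 0.5 and 1.0.

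**The case against.** The best defence is that *initial dosing* means the first dose at 30 mg. That is a fair reading for the post-dose part of Cmax and AUC, and it means those denominators are not made up of 15 mg exposure alone. It cannot rescue the trough, which precedes that dose, and it does not remove the carry-over.

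Three stronger inferences are tempting and are not supported:
- *The trough ratio will be about 2 whatever the true accumulation.* This needs proportional kinetics and the scheduled doses at both visits. Protocol 2.2.2 reports no clear dose-proportionality in the earlier Phase 2 study. Protocol Table 3 places transaminase rises usually at 3 to 6 weeks, so some patients may already be off 15 mg daily by Day 43.
- *The plan will report an AUC ratio that badly understates accumulation.* Scheduled samples stop at 4 h and parameters are calculated only if the data permit, so a 24 h AUC may not be computable. Where it is, the shortfall is trivial at a short half-life (1.04 against 1.08) and large only at a long one.
- *Stratifying by Week 36 dose would be enough.* It would put a ratio of 2.0 and one of 34 in the same group.

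It also stands that the formulas show Day 253 over Day 43 openly, that parameters are listed by patient, and that time to steady state is assessed separately from troughs (SAP 7.2.6).

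**Conclusion.** The label is wrong as written. The trough ratio compares repeat-dose troughs across a scheduled dose change and does not measure accumulation. The Cmax and AUC ratios carry earlier exposure in the denominator; under linear kinetics, and where it can be computed, the 24 h AUC ratio is capped near 2. These statements about what each term contains rest on the documents. The numerical sizes, including the trough range of 0.06 to 34 across dose histories, rest on an assumed linear model and assumed half-lives.

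Severity is minor. The ratio is descriptive, is not among the endpoints in Protocol Table 4, and does not touch the primary analysis or the sample size.

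**What to change.** In SAP 7.2.7:
1. Rename the quantity *Week 36/Week 6 ratio* and delete the words *accumulation* and *initial dosing*.
2. List each ratio with the actual dose and frequency preceding both the Day 43 and the Day 253 samples. Summarise by that dose pair where numbers allow, not by Week 36 dose alone.
3. State that the Cmax and AUC denominators include carry-over from earlier dosing, and that none of the ratios is to be read as accumulation.
4. Give dose-normalised troughs, if at all, only as a supplementary summary, with the proportionality assumption and pre-treatment Mo stated.

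The cost is SAP wording and one extra summary. Start and end dates for each dose and frequency are already to be listed by patient (SAP 7.3.1), so no new data are needed. The drawback is small strata: with about 24 evaluable patients (Protocol 9.2), some dose pairs may support only a listing.
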